# **PROTOCOL SYNOPSIS**

Title of Study: Is a future single-centre clinical trial of home-based taVNS feasible in people with

rheumatoid arthritis (RA)?

#### Co-ordinating Investigator/ Site:

[name]

Auckland University of Technology North Campus

[name],

[name],

[name]

**Objectives:** The primary objective of this study is to determine if a future single-centre clinical trial of

home-based taVNS is feasible in people with rheumatoid arthritis (RA).

**Methods:** This is a 14-day intervention. To address the primary objective, we will conduct 3 combined assessment and intervention sessions at the North Shore Hospital and participants will be required to complete another 12 sessions at home.

Number of participants: 12

Inclusion criteria:

- Aged 18 years and over
- Diagnosed with adult-onset RA according to ACR/EULAR 2010 RA classification criteria
- Have the presence of at least 3/28 swollen and/or at least 3/28 tender joints with 1 tender joint being in the hand or wrist

#### Exclusion criteria:

- Ear infection (otitis media or otitis externa)
- Poor hand dexterity and no access to a helper at home who could assist in fitting the in-ear taVNS device and the respiration sensor strap

- Changes in oral or biologic disease-modifying antirheumatic drugs (DMARDs) in the last 4 weeks
- Have had intraarticular or intramuscular corticosteroids within 2 weeks prior to study entry
- Unstable dosing regimen of NSAIDs or analgesics in the last 2 weeks
- History of arrhythmia, myocardial infarction in the last 12 months, currently on beta-blocker medication or history of stroke affecting the brainstem
- Previous vagotomy
- Currently implanted electrical and/or neurostimulator device
- Active malignancy or history of active malignancy in the last 2 years, with the exception of nonmelanoma skin carcinoma or carcinoma in situ
- Severe comorbidities which in the judgement of the study physicians would deem the participant not suitable as it may impact the safety of study conduct
- Known cognitive impairments
- Psychiatric illness with active psychosis
- Pregnant

Data Collection: During the intervention, all participants will wear the prototype taVNS device that contains the auricular stimulation electrodes placed on the concha of their left ear, an HRV sensor on their left index finger and a respiration sensor strap. During the 1st, 8th and 15th day visits, a 1-hour assessment will take place, whereby resting HRV, patient-reported outcomes, quantitative sensory testing and a blood sample of the participant will be collected for the evaluation of inflammatory biomarkers.

**Data Analysis:** During the 1st, 8th and 15th day visits, patient-reported outcomes and quantitative sensory testing results will be logged for each participant in a log file. The results of blood sample assessments will also be added to the above log file.

A user application will log and upload all the heart rate sample data for each session to Exsurgo's secure cloud infrastructure for each user. These data will stay in a secure location and will be post-processed for analysis.

#### Statistical Analysis:

Feasibility outcomes will be reported for

- **Participant eligibility and recruitment:** This will be reported based on the people with RA screened, ineligible, eligible, consented and declined.
- Intervention adherence: Reported by the number of sessions completed out of 14.

- Usability and Acceptability: Scores from usability and acceptability questionnaires will be evaluated.
- Estimates of mean intervention effect and variance: Intervention effect sizes will be calculated from baseline to 7 sessions and baseline to 14 sessions for the patient-reported scores, HRV parameters of RMSSD and HF-HRV and blood inflammatory biomarkers.
- Adverse events/safety: Safety-related events and withdrawals will be reported in absolute numbers and as a percentage out of 12 participants.
- **Relationships between HRV biomarkers and pain measures:** A correlation between changes in HRV and changes in pain and pain sensitivity will be reported.

# Background

# Transcutaneous auricular vagus nerve stimulation (taVNS) as an alternative treatment for managing pain

Current treatments for chronic pain are difficult to access and often only partially effective. There is a need for novel, more efficacious therapeutic approaches, particularly those that can be delivered remotely and/or facilitate self-management of pain and other symptoms. Neuromodulation is a fast-growing area that enables modulation of the central or peripheral nervous system circuits by delivering electrical, magnetic, optical, acoustic or mechanical energy to the body [1]. Transcutaneous auricular vagus nerve stimulation (taVNS), a type of neuromodulation, is a potential non-pharmacological alternative to manage pain. Vagus nerve stimulation activates several brainstem regions involved in descending pain inhibition [2], [3], likely increases the release of endogenous opioids [4], may alter nociceptive processing at a cortical level and has anti-inflammatory effects [5]–[7]. All these actions have been hypothesised to have an antinociceptive effect [8], [9]. taVNS is also advantageous in terms of feasibility and costs. An auricular device can be made small enough to be housed in a pocket-size or inear enclosure that is highly portable, allowing the treatment to be administered remotely or as a self-management device at home.

While there are several commercially available taVNS devices [10]–[14], only one of them offers closedloop stimulation [10]. Closed-loop stimulation enables automatic modification of stimulation parameters while reducing the need for manual intervention and monitoring of the effects of stimulation. For example, a continuous glucose monitoring system tracks the blood glucose levels and adjusts insulin injection doses to maintain the blood glucose levels within a therapeutic range. In this way, a closed-loop design has the theoretical advantage of ensuring a standardised therapeutic dose of taVNS based on its physiological effect, rather than the potentially inconsistent stimulation delivered by open-loop devices. To enable closed-loop stimulation, it is essential to establish one or more potential biomarkers that can be monitored to assess the effects of stimulation.

In addition, the ability to deliver taVNS in synchronisation with the exhalation phase of the respiratory cycle is likely to improve its application for pain management. Activity in the vagal brainstem nuclei is cyclically modulated by respiration [3]. Recent functional magnetic resonance imaging (fMRI) studies [5],[15] have shown exhalation respiratory-gated auricular vagal nerve stimulation (eRAVANS) evoked fMRI signal increase in brain regions associated with enhanced VN activity and descending pain modulation.

#### Why target people with RA?

RA is an autoimmune disease, the most common form of inflammatory arthritis and frequently leads to recurrent or chronic pain and disability. Inflammation within the joint contributes to the activation of peripheral nociceptors, leading to neuroplastic changes in both peripheral and central nervous systems [16]. There is also evidence that pain in RA can persist in the absence of overt inflammation, which is thought to be driven largely by central sensitisation, including impaired descending modulation of nociceptive pathways [17]. Also, lower HRV is associated with increased reported pain and increased inflammation in people with RA [18]. Hence, people with painful RA may have ongoing inflammation, impaired descending modulation of nociceptive pathways and evidence of ANS dysregulation, making them a good candidate population for taVNS.

#### The prototype taVNS system

We intend to design and build a novel taVNS device that is capable of synchronising stimulation with the exhalation phase of the respiratory cycle and uses real-time HRV as feedback for monitoring the physiological effects of stimulation. While possible to do this in a laboratory environment using existing gold standard equipment (e.g. 12 lead ECG to measure HRV parameters and a respiration strap to measure the respiration phase), it would be preferable to develop alternative, more portable methods of measuring HRV to allow the future taVNS device to be used more easily in both clinical and home-based settings. An alternative way of measuring heart rate and HRV is through the use of photoplethysmography (PPG), where inexpensive and non-invasive optical sensors are placed on the skin and infrared light is used to derive measures of heart rate [19], [20]. From these measures, it is possible to calculate HRV parameters [21], [22].

This study will inform if the prototype device is feasible to be used in a future single-centre clinical trial of home-based taVNS in people with RA.

#### **Objectives**

- 1. To determine if a future single-centre clinical trial of home-based taVNS is feasible in people with RA. This will be determined by
  - a. Estimating the proportion of patients with RA that meet the eligibility criteria.
  - b. Estimating how many eligible patients can be recruited.
  - c. Estimating the intervention adherence based on the percentage of the taVNS sessions started and completed.

- d. Evaluating the usability challenges and acceptability of in-home use of the prototype system and the user application.
- e. Identifying any adverse events/issues related to safety.
- 2. To explore potential dose-response relationships by estimating the mean intervention effect and variance on
  - a. Pain intensity (resting visual analogue scale (VAS), gripping VAS)
  - b. Pain sensitivity (pressure pain threshold)
  - c. Pain interference (Brief Pain Inventory)
  - d. Psychological distress (Depression, Anxiety and Stress Scale [DASS-21])
  - e. Health assessment (PGA [patient global assessment of disease activity] and HAQ [health assessment questionnaire])
  - f. C-reactive protein (CRP), Tumor Necrosis Factor-α (TNF-α), Interleukin (IL)-1β, IL-10 and IL-17A
  - g. Resting vagal tone (RMSSD, HF HRV), based on the assessment after the 7th and the 14th session.
- To determine whether HRV is a feasible biomarker for a future closed-loop taVNS device, we will explore the relationships between immediate post-taVNS change in HRV parameters and pain and pain sensitivity measures.

#### **Study Design**

A single-arm, repeated measures feasibility study will be undertaken. Participants will receive 14 sessions of daily taVNS for 20 minutes. Two of these sessions will be supervised and take place at North Shore Hospital, as part of an assessment session, while 12 of these sessions will be completed unsupervised, in the participant's home. The participants will be required to visit North Shore Hospital for three 1-hour assessment sessions on day 1, day 8 and day 15, during which patient-reported outcomes, resting HRV, quantitative sensory testing and a blood sample of the participant will be collected for the evaluation of inflammatory biomarkers.

#### Location

The study will be conducted at the North Shore Hospital and in the participant's home.

#### **Participants**

Twelve participants will be recruited from the Rheumatology outpatient departments in the Auckland region. This sample size is based on the number of participants that have been considered feasible to

recruit over 6 months rather than any formal power calculation. Participants will be included based on the following criteria:

- Aged 18 years and over
- Diagnosed with adult-onset RA according to ACR/EULAR 2010 RA classification criteria
- Have the presence of at least 3/28 swollen and/or at least 3/28 tender joints with 1 tender joint being in the hand or wrists

Participants will be excluded from the study if they have any of the following:

- Ear infection (otitis media or otitis externa)
- Poor hand dexterity and no access to a helper at home who could assist in fitting the in-ear taVNS device and the respiration sensor strap
- Changes in oral or biologic disease-modifying antirheumatic drugs (DMARDs) in the last 4 weeks
- Have had intraarticular or intramuscular corticosteroids within 2 weeks prior to study entry
- Unstable dosing regimen of NSAIDs or analgesics in the last 2 weeks
- History of arrhythmia, myocardial infarction in the last 12 months, currently on beta-blocker medication or history of stroke affecting the brainstem
- Previous vagotomy
- Currently implanted electrical and/or neurostimulator device
- Active malignancy or history of active malignancy in the last 2 years, with the exception of nonmelanoma skin carcinoma or carcinoma in situ
- Severe comorbidities which in the judgement of the study physicians would deem the participant not suitable as it may impact the safety of study conduct
- Known cognitive impairments
- Psychiatric illness with active psychosis
- Pregnant

Participants will be free to withdraw from this study at any time without affecting their right to receive further treatment. In addition, participants may be withdrawn after the initial assessment session(s) if the study team determines that they do not have sufficient finger dexterity to fit and operate the equipment at home or a person living with them who is able to assist them. Finally, participants may be withdrawn if the study physicians ([name], [name]) consider it inappropriate for them to continue for any reason, including intervention-emergent adverse events, a serious adverse event, or medical reasons unrelated to the study. Reasons for withdrawal will always be documented and reported.

#### Intervention

Participants will be asked to complete one 20-minute session of taVNS each day during the 14-day intervention period, using a specially developed prototype system. A user application, developed to accompany the prototype system, will be loaded on a mobile tablet that will be supplied to the participant. The application will instruct the participant to be seated in a chair and fit the equipment appropriately. It will check that the finger pulse sensor and respiration belt have been worn correctly and are transmitting the data to the application. The application will set the taVNS stimulation intensity to ensure it is strong but not uncomfortable. During each taVNS session, the stimulation will be administered for 1.0 second during exhalation only, and the HRV parameters will be continuously recorded by the application for a total of 20 minutes, after which the session will be completed.

#### **Other treatments**

In addition to taVNS, participants will receive usual care as deemed appropriate by the study physicians ([name], [name]), provided this is stable in the 4 weeks leading up to the baseline assessment and throughout the 14-day intervention period. Usual care may include medications and other regular treatments deemed appropriate by the study physicians. Changes to existing medications (e.g. DMARDs, corticosteroids) will not be permitted during the 14-day intervention period.

#### **Study Procedures**

Following screening and informed consent, participants will be booked in to visit the laboratory at the North Shore Hospital for three assessment sessions (Day 1, Day 8, Day 15). Blood samples will be taken at the beginning of each assessment session to track the changes in inflammatory biomarkers for the duration of the intervention. Patient-reported outcomes (e.g. Brief Pain Inventory, DASS-21,) will then be collected. A supervised 20-minute taVNS session will then be undertaken, with appropriate instruction. As part of the induction during the first assessment session, participants will be trained on how to insert the stimulation electrodes in the left ear and how to position the heart rate sensor. They will also be instructed on how to wear the respiration sensor strap. If the participant has poor hand dexterity that would make it difficult for them to fit/wear the in-ear taVNS device and the respiration strap (e.g. they report being unable to fit in-ear headphones by themselves) then they will be asked to be accompanied by a person living with them who can assist them in the fitment of the equipment during the home sessions. Before and immediately after 20 mins taVNS at each assessment session, pain at rest (VAS), pain during a standardised movement (VAS completed after 5 repetitions of 5kg grip) and pressure pain

thresholds will be assessed. An algometer (SBmedic, Sweden) will be used to assess the pressure pain threshold at two sites, the wrist of the dominant hand and the contralateral tibialis anterior (in a randomised order) at a ramping rate of 30kpa/sec. To assess pressure pain threshold, pressure will be increased until the participant feels any pain, at which point they will push a button. A mean of two measurements will be taken at each site, with a 30-second rest between repetitions.

After the first assessment session, participants will carry the equipment kit home. This kit will include the prototype system with a finger pulse sensor, a respiration belt, a commercial taVNS (Vagustim) device, a tablet running the mobile application and alcohol wipes. The finger pulse sensor and respiration belt have been chosen after the completion of a prior study conducted from April to July 2023 at Auckland University of Technology's North Shore campus. This study was approved by the AUT ethics committee. It recruited 35 participants who wore these sensors along with additional sensors for a duration of 60 to 90 minutes. The finger pulse sensor demonstrated excellent correlation (> 97%) and acceptable accuracy (24% error margin), with 95% confidence intervals and a p-value of < 0.001, in measuring the participant's heart rate variability when compared to a 12-lead electrocardiogram (ECG) system. The respiration belt achieved a true positive rate of 85%, with 95% confidence intervals and a p-value of < 0.001, in measuring the sensoring the start of exhalation when compared to a gold standard respiration belt. These sensors will be housed in the sensor box shown in the following figure.

The participant will be required to complete 12 further 20-minute sessions at the rate of 1 session/day over the next 14 days and return to the North Shore Hospital laboratory for 2 more occasions for assessments, with the equipment kit. Participants will be provided with the researcher's contact details for any kind of technical support or other assistance required.

Figure 1. Participant kit containing a 10-inch mobile tablet, Vagustim device with custom left ear electrode, sensor box with connections to finger sensor, respiration belt and power bank.

Treatment adherence, including completion of daily sessions, will be automatically captured by the mobile application. If participants miss a single session, a follow-up text message and email will be sent reminding them to complete the next session as planned. If participants fail to complete 2 consecutive sessions, a follow-up phone call will be made by a member of the study team to encourage adherence and troubleshoot any issues with the training. A phone number and email address will be made available for participants to seek technical assistance throughout the intervention.

Additionally, the responses to the questionnaires completed during each hospital visit will be evaluated within 24 hours. If the responses indicate a moderate or severe concern (eg. scores from the DASS21 form indicating moderate to severe stress or depression), the clinical team involved in the study will be notified. They will contact the participant to discuss the findings and notify their GP if needed.

In addition to other patient-reported outcomes, participants will be asked to complete short usability and acceptability questionnaires during the final assessment session (Day 15) to get feedback on the use of the prototype taVNS system at home. The usability questionnaire will ask the participants to rate the usability questions on a scale of 1 (Strongly Agree) to 10 (Strongly Disagree). These questions will be based on the guidelines provided from a systematic review of e-health applications [23] and a study evaluating the usability of mobile health applications by participants suffering from chronic health conditions [24].

The acceptability questionnaire will be based on the theoretical framework of acceptability [25] for healthcare interventions. The responses to this questionnaire will be rated on a scale of 1 to 5 with ratings of 4 or above suggesting general acceptability.

The following figures show the timeline of the study protocol for the 2 weeks and the flow of the user application from the start to the end of the session.

DestVAG		DestMAR		Destation	
Rest VAS,		Rest VAS,		Rest VAS,	
Grip VAS,		Grip VAS,		Grip VAS,	
Pressure pain		Pressure pain		Pressure pain	
threshold		threshold		threshold	
20 min		20 min		20 min	
taVNS		taVNS		taVNS	
Rest VAS,		Rest VAS,		Rest VAS,	
Grip VAS,		Grip VAS,		Grip VAS,	
Pressure pain		Pressure pain		Pressure pain	
threshold		threshold		threshold	
Blood		Blood		Blood	
samples &	20 min	samples &	20 min	samples &	
Questionnaires	taVNS	Questionnaires	taVNS	Questionnaires	
Day 1	Days 2 - 7	Day 8	Days 9 - 14	Day 15	→ Da

Figure 2. Study protocol for the 2 weeks, outlining the flow of events during the 3 hospital visits.

Figure 3. User application flow during a taVNS session.

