#### **Outcome measures**

**Participant eligibility and recruitment:** A log will be kept documenting the number of people with RA screened, ineligible, eligible, consented and declined. Feasibility outcomes will be reported on

- The proportion of screened people with RA who meet the inclusion criteria as a percentage of the total screened people
- The percentage of eligible participants that consented to be a part of the intervention

**Intervention adherence:** The user application will record the number of taVNS sessions started and completed. Adherence will be reported as a percentage of possible sessions completed prior to the final assessment (out of 14).

**Usability and Acceptability:** Individual items and total scores from both questionnaires will be evaluated. Overall acceptability of 60% or higher will be considered adequate, given the prototype design.

Adverse events/safety: Any participant withdrawals, reasons for withdrawal and any interventionemergent adverse events during the intervention period will be documented and reported both in absolute numbers and as a percentage out of 12 participants. An intervention-emergent adverse event (TEAE) will be considered any unfavourable and unintended sign (including an abnormal laboratory finding), symptom, or disease that occurs during the intervention period and may or may not be considered related to the intervention. During the Day 8 and Day 15 assessment sessions, participants will be asked the open question: 'Have you experienced any health problems or had any unusual symptoms or abnormal changes in bodily function in the last week?' If the participant answers yes, they will be asked to list any health problems/symptoms/changes in body function they have experienced, and a series of follow-up questions will be posed for each problem identified including: Can you describe it? When did it start? How long did it last for? How frequently did you experience it? Are you still experiencing it? Did it affect your usual daily activities? In what way? Did you seek any medical treatment? If so, what was this? This information will be used to create a TEAE log and then to classify and grade each TEAE using the Common Terminology Criteria for Coding Adverse Events (CTCAE).

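### Usability and acceptability are rated only at Day 15 and not at withdrawal, so the Objective 1d result could be too favourable if people stop because of the device

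*Protocol*

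**What the plan says.** Usability and acceptability form component (d) of the primary objective: "Evaluating the usability challenges and acceptability of in-home use of the prototype system and the user application" (Protocol, Objectives).

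Both questionnaires are scheduled once. Study Procedures states that "participants will be asked to complete short usability and acceptability questionnaires during the final assessment session (Day 15"). The Protocol describes no administration at Day 8, no early-termination visit and no remote completion.

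The acceptability items are "rated on a scale of 1 to 5 with ratings of 4 or above suggesting general acceptability" (Study Procedures). The usability items run from 1 for strong agreement to 10 for strong disagreement. Outcome measures then sets the mark: "Overall acceptability of 60% or higher will be considered adequate, given the prototype design". It does not say what the 60% is a percentage of.

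The Participants section lets people leave at any time and allows the study physicians to withdraw them, including for adverse events. It also foresees a reason tied to the device: "participants may be withdrawn after the initial assessment session(s) if the study team determines that they do not have sufficient finger dexterity" to use the equipment at home and have nobody to help. Withdrawals and adverse events are to be reported "both in absolute numbers and as a percentage out of 12 participants" (Outcome measures).

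**The concern.** Whether the questionnaires are completed depends on attending the last visit, and some of the foreseen reasons for not attending are failures of the very thing being measured. A person who stops because the system is hard to fit, unpleasant or not worth the effort would probably rate it poorly. If that person gives no rating, those who do reply are a favourable selection.

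This affects a component of the primary objective, and acceptability is the one feasibility component with a stated adequacy mark. With 12 participants, each lost rating is 1/12 = 8.3% of the sample. The gap lies in data collection: a statistical analysis plan can choose a denominator, but it cannot supply ratings that nobody asked for.

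**Working it through.** The Protocol has no power, dropout or precision figure to reproduce. The sample size rests on recruitment over six months: "This sample size is based on the number of participants that have been considered feasible to" recruit in that time. What follows is a sensitivity illustration.

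**Inputs from the Protocol.** Planned number N = 12 (Participants); acceptability mark 60% (Outcome measures); one rating occasion, Day 15 (Study Procedures).

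**Assumptions, not in the Protocol.** (i) The number of withdrawals w runs from 0 to 4. (ii) The 60% means the share of participants who find the system acceptable. (iii) Those who withdraw miss Day 15 and would not have accepted.

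**Step 1: smallest passing result among those rated.** With c = 12 − w completers, the smallest number of acceptors k is 0.60 × c rounded up to a whole number.

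| w | c | 0.60 × c | k | k/c | k/12 |
|---|---|---|---|---|---|
| 0 | 12 | 7.2 | 8 | 66.7% | 66.7% |
| 1 | 11 | 6.6 | 7 | 63.6% | 58.3% |
| 2 | 10 | 6.0 | 6 | 60.0% | 50.0% |
| 3 | 9 | 5.4 | 6 | 66.7% | 50.0% |
| 4 | 8 | 4.8 | 5 | 62.5% | 41.7% |

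With all 12 as denominator, 8 acceptors are always needed. Seven acceptors out of 12 fail (58.3%), but if one of the five others is lost before Day 15, the same seven pass (7/11 = 63.6%).

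**Step 2: what drives the gap.** Let p_c be the share accepting among completers and p_w the share among those who withdraw. The completers' share exceeds the share of all 12 by (w/12) × (p_c − p_w). For w = 2, p_c = 0.60 and p_w = 0, this is (2/12) × 0.60 = 0.10, or 60% against 50%. The gap is zero if w = 0 or p_w = p_c. It halves if those who withdraw accept at half the completers' rate.

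**Step 3: chance of meeting the mark.** Add the assumption that 50% of all 12 would accept (6 of 12), so that completers accept independently with probability 6/c. The chance of passing is P(X ≥ k), with X binomial (c, 6/c).

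| w | Completers' share 6/c | P(pass), completers only | P(pass), 8 of 12 needed |
|---|---|---|---|
| 0 | 50.0% | 0.194 | 0.194 |
| 1 | 54.5% | 0.385 | 0.183 |
| 2 | 60.0% | 0.633 | 0.167 |
| 3 | 66.7% | 0.650 | 0.143 |
| 4 | 75.0% | 0.886 | 0.100 |

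**Step 4: if the 60% refers to scores.** Steps 1 and 3 then do not apply, but the direction is unchanged. If ten completers average 4.0 and two withdrawn participants would have scored 2.0, the mean over all 12 is (10 × 4.0 + 2 × 2.0)/12 = 3.67.

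**Direction on the usability scale.** Because 1 is strong agreement, a favourable bias lowers the score if the items are positively worded. The item wording is not given.

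**The case against.** The strongest reply is that the problem may never arise. Treatment lasts 14 days, one missed session triggers a text and an email, two consecutive missed sessions trigger a phone call, and no dropout is predicted. If all 12 attend Day 15, there is no bias. This stands: the bias is a possibility that the plan leaves open. The Protocol is also silent on whether a withdrawn participant may still attend Day 15, so a reader who infers that none would do so goes beyond the text. Equally, nothing provides for it.

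The signal is also partly visible elsewhere. Withdrawals and their reasons are reported, and the application logs sessions started and completed. Feasibility rests on components 1a to 1e together, and no text makes the 60% mark decisive alone. This too stands as mitigation, but none of that information enters the usability or acceptability scores. The qualitative interviews mentioned under Data management have no stated procedure, timing or population.

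Poor dexterity without a helper is already an exclusion criterion, and Objective 1d concerns use at home. Someone withdrawn straight after the Day 1 visit may have no home use to rate. That weakens the dexterity example, but not the case of someone who stops after several home sessions.

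A reader might also take the different denominators as an error, with safety out of 12 and questionnaires from attenders. They are not: feasibility outcomes ordinarily have different denominators, the Protocol states the one for safety, and the one for acceptability may be set in an analysis plan that is not at hand.

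**Conclusion.** The concern holds in conditional form. The Protocol ties the only usability and acceptability ratings to attendance at Day 15, foresees withdrawals related to the device or its tolerability, and describes no collection at withdrawal. If anyone leaves for such a reason and misses Day 15, the Objective 1d result could be biased in a favourable direction.

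The illustrated size, a passing result equal to anything from 58.3% down to 41.7% of the 12, rests on three assumptions that the Protocol does not supply: one to four withdrawals, the 60% read as a share of participants, and no acceptance among those who withdraw.

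A reader might infer that the plan would let the system pass when only a minority of those enrolled accept it. On these assumptions that occurs at four withdrawals; with two or three the smallest passing result is exactly half of 12, and with one it is above half. The missing collection point is certain from the text; the bias and its size are not.

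**What to change.** Add to Study Procedures that both questionnaires are also given at the point of withdrawal, by phone, on the supplied tablet or when the kit is returned. Offer them to everyone who has used the device, and at least to those who took the kit home.

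In Outcome measures, state what the 60% is a percentage of. Report acceptability among all participants with a rating, next to the number who started and the number without a rating. Add a sensitivity analysis that counts missing ratings as not acceptable. It should not be the main rule, because it would also penalise withdrawals for medical reasons unrelated to the study. The safety denominator need not change.

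The cost is a few sentences of Protocol wording and a few minutes per withdrawing participant. The reported figure may be less favourable.
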